5.2.5 Testing procedures in the laboratory

At the laboratory, aliquots of the venous blood sample will be used to run an additional replicate of the SBD POC test and reference tests in duplicate. Depending on availability, additional POC G6PD tests that are both commercially available and currently under development may be run as well. Hemoglobin [Hb value (g/dl)] will be determined within 24 hours using a hematology analyzer for each sample to estimate the G6PD activity. Aliquots of the venous blood will be used for running the spectrophotometric assay (reference standard) and the fluorescent spot test (FST). The reference assay, hemoglobin, and replicate of the G6PD quantitative test will be conducted at the same time. A thermometer and a hygrometer will be placed at the study site near the assays. Temperature and humidity will be observed at the time the tests are run and recorded in the study database.

[figure not shown]
Test operators in the laboratory will be blinded to the results of the POC tests obtained and recorded in the field and operators of the reference assay will be blinded to the results of the replicate POC test run on venous sample. If there is a discrepancy between the results of the reference assay replicates, greater than allowed by the TPP, testing will be repeated. Performance characteristics and the results of additional testing of samples with discrepant results will be reported as per WHO technical specifications [15].

Leftover sample will be stored for possible confirmatory or additional testing. Depending on availability of additional novel G6PD tests at the time of study start, additional assays may be run on remaining samples. If additional POC G6PD tests are added, in particular tests that are under investigation and not registered for use in Brazil, the study team will amend the protocol and advise the ethical review boards and appropriate regulatory authorities. For all novel assays to be included in the study, appropriate regulatory procedures will be followed in order to include the assays for research purposes only.

This includes products that not yet commercially available and products that are commercially available but are not part of the standard of care at the clinic site. In the event the stored sample is used, the Fundação de Medicina Tropical [name] Dourado (FMT/HVD) and Fiocruz will be responsible for obtaining the necessary ethical approvals.

For a summary of tests to be performed on the samples, see Figure 2.

Figure 2. Diagnostic performance assessment process

5.3 Specimen collection, transport, and storage

Immediately after collection, whole blood in EDTA will be stored in a refrigerator or a cooler box and transported to the lab. Samples from each region will be tested at a laboratory that will be established locally to provide reference testing within the given period. In the lab, each specimen will be immediately aliquoted as below.

- Aliquot 1 x 2ml whole blood in a falcon tube or conical screw cap tube. Store at 4 degrees Celsius in the refrigerator. This will be used for all assays. Specimens should be kept refrigerated (2-8°C) prior to testing for up to 72 hrs. Any remaining specimens will be discarded 3 weeks after collection.
- Aliquot 4 x 0.5ml whole blood in cryogenic tubes. Save at -80C in freezer. Maximum storage time is 10 years after study end. This leftover sample will be stored for possible additional testing at FMT/HVD. Appropriate permission for additional testing relating to malaria will be obtained through the consent process.

5.4 Test result return and follow up

Results of point of care malaria microscopy will be returned to participants as per standard care. Results of the POC hemoglobin testing will be returned to participants

immediately after testing, as the test is registered for use in Brazil. Study staff will relay results and counsel participants who test positive for malaria or anemia according to the results return script (Appendix C3). Any participants identified as malaria positive or anemic will be counselled and referred for follow-up. Participants in the clinic will receive standard care at the clinic and participants recruited through household surveys will be referred for follow-up to the local health agent as per routine practice.

In Brazil, no routine screening to identify individuals with G6PD deficiency is implemented in the public health system and treatment with primaquine is recommended for all people infected with *P. vivax* with the exception of pregnant women and children under six months of age. However, information regarding the G6PD status of a vivax patient is critical for informing safe and effective treatment recommendations. As per WHO guidelines for the treatment of malaria, standard treatment of primaquine should not be given to patients who are G6PD deficient in order to avoid primaquine-induced hemolysis and patients who are G6PD intermediate should be monitored closely for signs of hemolysis [18].

Initial evaluations by PATH indicate that the POC G6PD test is able to identify G6PD deficiency (see section 7.1). As such, participants who test positive for *P. vivax* malaria and are found to be G6PD deficient or intermediate will be notified of their POC test result in order to make that information available to their health provider when determining their course of treatment for vivax malaria.

Participants found to be vivax positive and G6PD deficient

For vivax positive participants found to be G6PD deficient with the POC test (G6PD test result of below 30% of normal enzymatic activity), the study team will provide referral with the recommendation that primaquine treatment be withheld until confirmatory testing can be completed. Confirmatory testing will take no more than one week to complete. At that time, through referral to the health agent, *P. vivax* patients who are identified as G6PD deficient can receive treatment for the blood stage disease (treatment with chloroquine) immediately.

If the results of the reference assay confirm the results of the POC G6PD test (enzymatic activity less than 30%) they will be contacted and informed of the result and their G6PD status by validated reference assay. If the results of the reference assay indicate that the participant is G6PD normal, they will be contacted, informed of the result, and referred to a health agent to receive with standard treatment for liver stage disease, as per national guidelines.

Participants found to be vivax positive and G6PD intermediate

For vivax positive participants found to be G6PD intermediate with the POC test (G6PD test result between 30 and 80% of normal enzymatic activity), the study team will provide referral with the recommendation that primaquine treatment be closely monitored for signs of hemolysis given the increased risk of hemolysis associated with moderate G6PD deficiency.

If the results of the reference assay confirm the results of the POC G6PD test (enzymatic activity between 30-80%) they will be contacted and informed of the result and their G6PD status by validated reference assay. If the results of the reference assay indicate that the participant is G6PD normal, they will be contacted and informed of the result and referred to a health agent to receive with standard treatment for liver stage disease, as per national guidelines.

Among any vivax positive participants, those known to be G6PD intermediate or deficient based on previous studies may receive a false negative result on the POC investigational test in this study and found to be G6PD normal. In the event that this occurs, the study team will proceed in the same manner as for participants found to be vivax positive and POC G6PD deficient or intermediate. See Figure 3.

Participants will be notified at recruitment that the study team will tell them the results of the G6PD test only if they are found to be G6PD intermediate or deficient. For participants who do not have *P. vivax* malaria, confirmatory testing will be done prior to informing the participant of this result. Participants who are found to be G6PD normal by the reference assay will not be notified of their result unless they were notified of a G6PD deficient and/or intermediate result by the POC test that needs to be corrected. If they were reported a false positive result from the POC test and found to be G6PD normal by the reference assay, the study team will follow up and provide the results of the reference assay and necessary counselling. Any participants found to be G6PD intermediate or deficient will be contacted by the study team to provide counselling and given a card with further information for patients and providers (Appendix C2).

[figure not shown]
The study team will inform the participant that G6PD is a genetic condition and recommend that they may want to encourage their family to be tested as well. The study team will inform participants where and how their immediate family members can be tested free of cost. The card describes G6PD deficiency as it relates to contraindicated medications and other risk factors such as foods. The research team involved in the return of G6PD test results have significant experience working in G6PD research and counselling study participants as to the results. All staff involved in returning these results will receive dedicated refresher training aimed at providing the necessary information and delivering it in a way that facilitates comprehension.

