2.0 Study objectives

The hypothesis of this study is that the rapid test for G6PD and Hemoglobin, SD Biosensor, has equal accuracy by means of a comparison with the gold standard and high level of usability and acceptability among healthcare professionals who will execute it. The goal of this study is to contribute to a body of evidence that will support the submission of G6PD tests to the WHO PQ process and for product registration in target countries.

The primary objective is to assess the accuracy and reliability of G6PD tests in detecting G6PD activity and classifying results when used by trained health care workers.

Component objectives include:

- To determine the performance of G6PD tests in detect G6PD activity compared to a reference assay
- To assess the comprehension of the G6PD test packaging and labelling among intended users
- To assess the usability of G6PD test result outputs among intended users

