3.1 Statistical analyses

Data will be entered into a Microsoft Excel database with built-in validation rules to minimize data entry errors. Descriptive statistical analysis, including calculating point estimates, distribution, and frequencies of responses, will be used to summarize and characterize the study population.

3.1.1 Diagnostic accuracy and performance:

For the purposes of this study, an individual will be considered G6PD deficient (case) if they test positive by the spectrophotometric gold standard. The primary success criterion will be focused on the ability to identify G6PD deficient participants correctly, such that both the POC G6PD test and the spectrophotometric gold standard test should both accurately identify all G6PD deficient specimens (with < 20% normal) as deficient.

The performance of the POC G6PD against the spectrophotometric gold standard will be determined by calculating the sensitivity and specificity. Sensitivity and specificity of the SD Biosensor (SDB) G6PD assay were calculated as per Domingo et al. [14]. In summary, an adjusted male median will be calculated for both the POC G6PD and spectrophotometric gold standard test from where the 30%, 40%, 70% and 80% cutoff levels for the two tests will be used to categorically define G6PD deficient cases.

Sensitivity calculations will be determined by the following method: TTP=true and test positive (positive by reference assays according to case definition and positive by the POC G6PD test), FNTP=false negative true positive (positive by reference assays according to case definition and negative by the POC G6PD test). Sensitivity = $TTP/(TTP+FNTP)$.

Specificity will be determined by the following method: TPTN=test positive true negative (negative by reference assays according to case definition and positive by POC G6PD test), TTN=Test and true negative (negative by reference assays according to case definition and negative by POC G6PD test). Specificity= $TTN/(TTN+TPTN)$.

Sensitivity and specificity results will be reported using 95% confidence intervals.

3.1.2 Accuracy between G6PD activity and Hemoglobin methods:

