Quantitative agreement for both G6PD activity and Hb values between the POC G6PD test and spectrophotometric gold standard will be graphically analyzed. Correlation graphs between the POC G6PD test and gold standard test will be plotted and an R-squared value will be determined. An R-squared value of greater than 0.9 for both G6PD activity and Hb will be considered acceptable.

Bland Altman plots, where differences between the G6PD POC tests and gold standard test are plotted against the gold standard value, together with the 95% limits of agreement. Acceptable limits of agreements for Hb should be within +/-1.0 g/dL (based on a 6% estimate for allowable method bias) and for G6PD activity should be within +/-2.0 U G6PD/g Hb (based on a 15% estimate for allowable method bias). All statistical analyses will be performed using Stata 13.0.

The data comparison for the analyses is outlined below:

Table 1. Comparison methods

Index test by sample type	Reference method	
	G6PD normalized for Hb	Hb
Venous	Point Scientific G6PD from venous specimen normalized for Hb from venous specimen	Hb from venous specimen
Capillary		Hemocue Hb from finger stick

3.1.3 Diagnostic usability:

Response choices to usability assessment questionnaires will include both multiple-choice and open-ended responses. The usability questionnaire will include a brief assessment of health literacy using a validated health literacy instrument. Participants will be encouraged to comment on any aspects of the label or results they find confusing or inadequate. Success criteria are defined as 85% correct participant response to questions that assess key messages and results interpretation. Any participant that obtains 85% or above correct responses to the usability questionnaire will be considered to accurately comprehend the product IFU and labelling. Analyses will include descriptive statistics and a tabular presentation of findings.

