If any participants are confirmed *P. vivax* malaria positive and G6PD deficient at the point of care, the study team will relay this the information as part of the counselling. The study team will refer the participant to a health for treatment, equipped with counselling information that the participant may be G6PD deficient or intermediate and if given primaquine treatment is at an increased risk of severe hemolysis. This will enable the participant to receive immediate treatment for the blood stage infection and provide better information to the health worker responsible for case management, including any treatment for the liver stage infection. The participant's G6PD status will then be confirmed by a reference assay to inform further case management as necessary. The table below outlines the study procedure and subsequent follow up action.

Table 5. Case management

Study test	Result		Action
Hemoglobin	Normal hemoglobin levels (by national guidelines)		No action
	Mild moderate or severe anemia (by national guidelines)		Counselling re: the results of the hemoglobin test and referral to the health system for follow-up case management. This may involve the provision of iron tablets or other treatment depending on severity.
G6PD deficiency	Negative test result on investigational device (G6PD normal)		No immediate action. If reference assay is discrepant and identifies G6PD intermediate or deficient status, the study team will conduct follow-up counselling (Appendix C2).
	Positive test result on investigational device (G6PD deficient or intermediate)		Result to be confirmed at the laboratory with the reference assay. If confirmed G6PD deficient or intermediate with the reference assay, the study team will conduct follow-up counselling (Appendix C2).
Malaria	Negative test result (no malaria)		G6PD and hemoglobin managed as above, otherwise no action
	Positive test result (confirmed malaria)	POC G6PD normal	Patient referred to health system for free treatment: 3 days CQ and 7 days PQ. If confirmed deficient or intermediate with reference assay, provide follow up counselling as described above.
		POC G6PD intermediate	Patient referred to health system for free treatment: 3 days CQ and 7 days PQ. Provide counseling re: G6PD intermediate status and recommend additional monitoring and attention to possible signs/symptoms of hemolysis. If confirmed deficient or intermediate with reference assay, provide follow up counselling as described above.

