7.0 Study products

7.1 SDB G6PD Analyzer

The STANDARD G6PD Analyzer is designed to measure the quantitative determination of total-hemoglobin concentration and G6PD enzymatic activity in fresh human whole blood specimen based on reflectometry assays. The test is intended to aid in the identification of people with G6PD deficiency. The test is currently registered in Brazil but not used by the public health system or considered part of routine use in malaria case management. PATH has conducted some initial laboratory evaluations which suggest that the test aligns to performance specifications outlined in the target product profile [19]. The test has CE mark and is registered for use in other malaria endemic countries.

Performance STANDARD G6PD test when stress tested under multiple temperature and humidity conditions. The STANDARD G6PD values were compared to the Pointe Scientific generated G6PD values for all 314 data points generated across the following ambient conditions: 22 °C, 32 °C 50% humidity, 37 °C 50% humidity, and 37 °C 75% humidity. ROC analysis was performed to generate the optimal thresholds for the STANDARD G6PD test. CI refers to the confidence interval, NA, not applicable.

Table 7. Performance of SD Biosensor STANDARD G6PD test

Threshold (Pointe Scientific value U/gHb)	Optimal STANDARD G6PD (U/gHb)	Sensitivity (95% CI)	Specificity (95% CI)
30% (2.8)	4.2	100 (95.1 – 100.0)	96 (93.0 – 98.3)
70% (6.5)	6.0	98 (92.4 – 99.7)	99 (96.8 – 99.9)
80% (7.4)	6.2	86 (80.7 – 93.9)	99 (95.9 – 99.7)
100% (9.3)	NA	NA	NA

Figure 4. SD Biosensor STANDARD G6PD Test

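### Section 3.1.1 scores the POC test at percentages of its own study median, so it does not estimate the accuracy of the class that a health worker can assign, and section 5.4 acts on, at the visit

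*Combined protocol and SAP*

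**What the plan says.** The primary objective (section 2.0) covers "classifying results when used by trained health care workers". At the visit the POC class drives the referral. Section 5.4 recommends withholding primaquine when a vivax-positive participant is "found to be G6PD deficient with the POC test (G6PD test result of below 30% of normal enzymatic activity"), pending a reference result within a week. For a participant "found to be G6PD intermediate with the POC test (G6PD test result between 30 and 80% of normal enzymatic activity"), primaquine goes ahead under monitoring; Table 5 adds: "Provide counseling re: G6PD intermediate status and recommend additional monitoring and attention to possible signs/symptoms of hemolysis". Both limits are percentages of normal, and the protocol text gives no POC reading in U/g Hb for either.

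For the accuracy analysis, section 3.1.1 states that "an adjusted male median will be calculated for both the POC G6PD and spectrophotometric gold standard test", and that cutoffs at 30%, 40%, 70% and 80% of those medians define the classes. Its success criterion is that the POC and the reference "should both accurately identify all G6PD deficient specimens (with < 20% normal) as deficient".

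Section 5.4 points to section 7.1 as its reason for acting on the POC result. There, "ROC analysis was performed to generate the optimal thresholds for the STANDARD G6PD test", using 314 data points from four temperature and humidity conditions. Table 7 lists NA as the POC value at 100% activity.

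**The concern.** A health worker at the visit has one reading and cannot know the POC median of a study still under way. Any class assigned then must rest on a limit fixed beforehand. Section 3.1.1 scores a different class, set afterwards from the pooled readings. If the device reads systematically high or low against the reference, a fixed limit carries that error into the class, whereas a limit set from the device's own median largely absorbs it. The study could then report accuracy that users would not obtain, or understate what they would obtain.

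The care question is narrower. A reference-deficient participant whose POC class is intermediate or normal is referred for primaquine, and the plan should say what happens when the reference result comes back.

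**Working it through.** **1. Reproduce Table 7.** Inputs: reference 100% = 9.3 U/g Hb; reference limits 2.8, 6.5 and 7.4 (30%, 70%, 80%); optimal POC limits 4.2, 6.0 and 6.2. Check: 0.30 × 9.3 = 2.79, 0.70 × 9.3 = 6.51, 0.80 × 9.3 = 7.44. The reference limits are percentages of 9.3, as labelled.

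**2. POC median implied by each POC limit.** Limit ÷ percentage:
- 4.2 / 0.30 = 14.0
- 6.0 / 0.70 = 8.6
- 6.2 / 0.80 = 7.75

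No single median gives all three limits.

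**3. The 30% POC limit under assumed POC medians.** The POC median is not in the documents, so a range is needed:
- 0.30 × 7.75 = 2.3 (median implied by the 80% row)
- 0.30 × 8.6 = 2.6 (70% row)
- 0.30 × 9.3 = 2.8 (POC on the reference scale)
- 0.30 × 12 = 3.6

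All lie below 4.2. The two coincide only at a POC median of 14.0.

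**4. What scoring against the device's own median removes.** Suppose the POC reads k times the reference. Its median is k × 9.3 and its 30% limit is k × 2.79. A specimen with reference value r reads k × r, which is below k × 2.79 exactly when r is below 2.79. The classes agree perfectly whatever k is. At a fixed limit L the class depends on whether k × r is below L, so k matters. If the POC instead reads the reference plus a constant c, its 30% limit is 0.30 × (9.3 + c) = 2.79 + 0.3c, so three tenths of the shift is absorbed. Table 7 does not look purely proportional (4.2 / 2.8 = 1.5, but 6.2 / 7.4 = 0.84), so the two analyses may differ in either direction.

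**5. Reach into the success criterion.** Using 9.3, 20% of normal is 0.20 × 9.3 = 1.86 U/g Hb. The criterion requires every such specimen to be called deficient, so one reading between the two limits makes its outcome depend on the limit. The plan's tolerances give a range for a specimen at 1.86:
- Section 3.1.2 says agreement "for G6PD activity should be within +/-2.0 U G6PD/g Hb". The extreme reading is 1.86 + 2.0 = 3.86: deficient at 4.2, intermediate at 2.3-2.8.
- The same sentence bases this on a 15% bias: 0.15 × 1.86 = 0.28, so 1.86 + 0.28 = 2.14. That is deficient at every limit considered here.

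**6. Scale.** Section 3.2 expects about 100 deficient participants in Brazil. Each one whose reading falls between the field limit and the study-median limit changes sensitivity by 1/100 = 1 percentage point. How many would do so is not given.

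**7. Follow-up, set side by side.** For a POC-intermediate participant, section 5.4 covers reference intermediate and reference normal, but not reference deficient. Table 5 adds follow-up counselling if the reference shows deficiency, for POC intermediate and POC normal alike, with no date and no advice to stop primaquine. Section 5.6 describes 3 days of chloroquine and then 7 days of primaquine, so primaquine would start on day 4. Section 5.4 allows confirmatory testing up to a week.

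**The case against.** **The field limits may exist.** The device is registered in Brazil, users are certified as proficient, and one endpoint is whether they can interpret and classify the output, which presupposes stated classes. The instructions for use, Figure 3 and the appendices are not in the copy reviewed. This stands: a reader should not infer that staff have no limits. It does not answer the analysis point, because section 3.1.1 as written would not score those limits.

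**Percent-of-median is the recognised method.** Section 3.1.1 follows a cited recommendation, and Table 2 attributes the same definition to WHO prequalification. This also stands, and it is why that analysis should be kept. It answers whether the device ranks people correctly relative to its own normal. The visit-day classification is a separate question.

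**Table 7 is weak evidence.** It pools stress conditions, and ROC optima need not fall at percentages of a median. A reader might infer that 100% sensitivity requires a POC limit of 4.2, which is 45% of 9.3. The documents do not show this: sensitivity at 2.8 is not reported, and 4.2 / 9.3 divides a POC reading by a reference-scale value.

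**The success criterion.** A reader might also infer that a device meeting the agreement limits could readily fail the criterion. The reading of 3.86 is a worst case; under the 15% basis the problem disappears.

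**Care.** Routine practice gives primaquine without G6PD testing, so the study does not add that risk. Deficient participants are contacted and given a card, and those with known deficient or intermediate status who read POC normal are handled as POC deficient or intermediate. Clinic participants of unknown status lack that last safeguard.

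**Conclusion.** The point holds as a mismatch between the class used and the class scored. Section 3.1.1 alone does not estimate the accuracy of the classification available to a health worker at the visit. Table 7 makes a difference plausible (4.2 against 2.3-2.8 U/g Hb), assuming a POC median of 7.75-9.3. The direction and size of the effect on sensitivity cannot be derived from the documents; any percentage loss would be an assumption. The documents do not support calling the percent-of-median analysis wrong, or requiring 4.2 and 6.2 as field limits. The missing follow-up instruction for POC-intermediate or POC-normal, reference-deficient vivax cases is a separate, smaller gap. This is a change the sponsor should make, and it is easy to make before enrolment.

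**What to change.** 1. Before enrolment, cite in section 5.4 and Table 5 the fixed U/g Hb limits used in the field and their source: the instructions for use, or another pre-stated source.
2. In section 3.1.1, pre-specify sensitivity, specificity and the success criterion for specimens below 20% of normal at those fixed limits, using the health worker's recorded capillary reading. Report them alongside the percent-of-median analysis. The reference classes can stay as percentages of the reference median.
3. In section 5.4, add that a vivax-positive participant who is POC intermediate or normal but reference deficient is contacted as soon as the reference result is available, if possible before the first primaquine dose, with advice to the provider to withhold or stop primaquine.

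The cost is protocol text, one extra results table from readings already recorded, and faster handling of reference results for vivax-positive participants. No new samples or visits are needed.

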5.5 Summary of study procedures

Table 6. Summary of study procedures

Participant group	List of study procedures	Estimated time	Data collection forms used
Health workers	
 • Training on the use of POC G6PD tests • Consent and enrolment • Usability assessment questionnaire 	
 • Up to 5 hours • 20 minutes • 20 minutes 	
 • Appendix A2
Children aged 2-18	
 • Assent, parental permission, and enrollment • Conduct POC tests and blood draw 	
 • 20 minutes • Up to 30 min 	
 • Appendix A1
Adults	
 • Consent and enrolment • Conduct POC tests and blood draw 	
 • 20 minutes • Up to 30 min 	
 • Appendix A1

Figure 3. Participant flow and follow-up procedures

*Vivax positive patients, recruited from the enriched sample of participants known to be G6PD deficient or intermediate, may receive a false negative G6PD normal result from the investigational POC test. In the event this occurs, this subpopulation will be considered G6PD intermediate/deficient and provided counseling and a counselling card as described in section 5.4.

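### Recorded G6PD status overrides the point-of-care result only after a normal reading, so a vivax patient recorded as deficient who reads intermediate is referred for primaquine with no hold

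*Combined protocol and SAP*

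**What the plan says.** All references are to the combined protocol and SAP.

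- **Known status, section 5.4.** Among vivax-positive participants, "those known to be G6PD intermediate or deficient based on previous studies may receive a false negative result on the POC investigational test" and so read normal. They are then to be handled as if the POC reading had been deficient or intermediate; the text does not say which of the two.
- **Known status, footnote to Figure 3 (section 5.5).** This repeats the rule, again for a falsely normal reading only: "this subpopulation will be considered G6PD intermediate/deficient" and is given counselling and a card.
- **POC deficient, section 5.4 and Table 5.** Primaquine is to be withheld until the reference result. For this route the text adds: "Confirmatory testing will take no more than one week to complete".
- **POC intermediate, section 5.4.** The route applies to a "G6PD test result between 30 and 80% of normal enzymatic activity", with no distinction by sex. Referral carries the "recommendation that primaquine treatment be closely monitored for signs of hemolysis". Table 5 sends the patient for both drugs with counselling and monitoring.
- **POC normal, Table 5.** The malaria-positive row sends the patient for both drugs and adds counselling if the reference assay disagrees. Recorded status is not mentioned.
- **The standard the protocol cites, section 5.4.** "standard treatment of primaquine should not be given to patients who are G6PD deficient".
- **Follow-up of any abnormal result, section 5.4.** "Any participants found to be G6PD intermediate or deficient will be contacted by the study team to provide counselling and given a card". "The card describes G6PD deficiency as it relates to contraindicated medications".

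**The concern.** About half the participants are to come from earlier surveys, so the study team already holds their G6PD status. The protocol accepts that this record should count when the investigational test reads normal. An intermediate reading in a person recorded as deficient may be the same kind of error, yet there the record plays no part. Followed as written, the plan can refer someone recorded as deficient for standard primaquine, against the guideline that section 5.4 cites. Staff who work from Table 5 would also miss the rule that does exist for a normal reading. What is at stake is avoidable exposure to a drug that can cause hemolysis in deficient people.

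**Working it through.** **Step 1. Recorded status against POC reading, vivax-positive participants**

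| Recorded status | POC reading | Section 5.4 and Figure 3 footnote | Table 5 |
|---|---|---|---|
| Deficient | Deficient | Primaquine withheld | Same |
| Deficient | Intermediate | No override; monitored primaquine | Both drugs, monitoring, no hold |
| Deficient | Normal | Override; route not specified | Both drugs; override absent |
| Intermediate | Normal | Override; route not specified | Both drugs; override absent |

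The second row is the gap. The third and fourth show both the unspecified route and the conflict with Table 5.

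**Step 2. Sex.** Table 2 gives females an intermediate class at 30% to 80% of the adjusted male median and calls males above 30% normal. A female recorded as deficient who reads in that band is plainly intermediate and outside the override. A male could be called normal under Table 2, which brings the override in, or intermediate under section 5.4, which does not.

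**Step 3. Primaquine doses before the reference result.** Section 5.6 gives three days of chloroquine followed by seven of primaquine. Assume referral on day 1, one primaquine dose a day on days 4 to 10, and the result reported at the end of day r. Then doses = max(0, min(7, r − 3)).

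| r | 1 to 3 | 4 | 5 | 6 | 7 |
|---|---|---|---|---|---|
| Doses | 0 | 1 | 2 | 3 | 4 |

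- Section 5.2.5 has hemoglobin measured within 24 hours and the reference assay run alongside it. With prompt reporting: 0 doses.
- Section 5.3 allows refrigerated storage for up to 72 hours before testing. That is the end of day 3 counted from the start of day 1, or during day 4 if the clock starts later, for example at receipt in the laboratory: 0 or 1 dose.
- The one-week limit would give 7 − 3 = 4 of 7 doses, but it is stated only for the POC-deficient route.

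**Step 4. Number affected.** Table 7 gives sensitivity at the 30% threshold as 100% (95% CI 95.1 to 100.0). At the lower limit, 100 − 95.1 = 4.9% of deficient samples read above the cutoff. Section 3.2 expects about 100 deficient participants: 0.049 × 100 = 4.9. The range is therefore 0 to about 5 over both recruitment streams, before requiring recorded deficiency and vivax infection. The documents give no vivax rate for the home-visit stream. If it is assumed to be 1% to 10%, even all 4.9 being recorded as deficient gives 4.9 × 0.01 = 0.05 to 4.9 × 0.10 = 0.5 people.

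Table 7 comes from laboratory stress testing at an optimised POC cutoff of 4.2 U/gHb, against 2.8 U/gHb for the reference 30% value (4.2 / 2.8 = 1.5). The visible text does not give the U/gHb cutoff for use in the field, so field misreads could be more frequent.

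**The case against.** The case on the other side has five parts.

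- **Comparison of routes.** A reader might infer that a participant recorded as deficient is protected less when reading intermediate than when reading normal. The documents do not show this. The override names both routes without choosing, and the footnote promises only counselling and a card. A normal reading is therefore not shown to bring a hold. This part stands, and the unspecified route is itself part of the point.
- **Timing.** A reader might infer that several doses, or all seven, would be taken before the result. Four doses need the one-week limit carried over to a route for which it is not stated. Seven would need primaquine to start with chloroquine, contrary to the order in section 5.6. For home visits, slides are read at the nearest facility and results are delivered later, so treatment may start after the blood draw and doses would be fewer still. This stands.
- **Follow-up.** A reader might infer that a deficient reference result after an intermediate reading leads to nothing. Section 5.4 already requires contact, counselling and a card covering contraindicated medications. Only an explicit recommendation to withhold or stop primaquine is missing.
- **Unseen material and local decisions.** The body of Figure 3 and Appendices C2 and C3 are not available and may cover part of this. Treatment decisions rest with the local health worker or clinic. Both lower the severity. Neither removes the gap in the visible text or the mismatch with Table 5.
- **Quality of the record.** The visible text does not give the method or cutoff of the earlier surveys, so ranking the record above a same-day quantitative reading is a judgement. That matters little for a rule that lasts only until the reference result.

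**Conclusion.** The point holds as a minor one. In the visible text the override is confined to a POC-normal reading and does not specify a route. A participant recorded as deficient who reads POC intermediate is referred for primaquine with monitoring and no hold, clearly so for females and ambiguously for males. Table 5's POC-normal row conflicts with section 5.4.

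The number affected is well under five and possibly none, if Table 7's laboratory performance carries over to the field. About 0 to 1 primaquine doses would precede a reference result that is reported promptly, assuming sequential dosing from the day of referral. The documents do not support reading this as a systematic hazard: few people are involved, monitoring and contact are already required, and prompt reporting would usually bring the result before the first primaquine dose.

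**What to change.** State one rule in section 5.4, the Figure 3 footnote and Table 5: until the reference result is back, a vivax-positive participant is managed by the more severe of recorded status and POC reading.

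- Recorded deficient, POC intermediate or normal: chloroquine, with a recommendation to withhold primaquine (the existing POC-deficient route).
- Recorded intermediate, POC normal: the existing monitoring route.
- Reference result deficient after POC intermediate or normal: the contact already required in section 5.4, made promptly and with a recommendation to withhold or stop primaquine.

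The cost is a few sentences and an amendment to the review boards, with no new test, visit or sample. If the earlier record was wrong, primaquine is delayed by at most about a week, since these participants would join the route to which the one-week limit applies. Chloroquine is not delayed.
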